13.3 Unanticipated Problems

- *Describe process for reporting any unanticipated problems to IRB, sponsor (if applicable), and FDA (if an FDA-regulated study).*

Participation and Environment Measure-Plus (PEM-Plus) Care Planning Intervention

NCT Number: 03820011

Date: June 17, 2017

Aim 1 Statistical Plan:

Demographic and usability data were exported via REDCap, and an administrative dashboard for analyses. Demographic characteristics and YC-PEM summary scores were reported for each user. To address the main study question, usability estimates were derived for the total study sample, according to technical effectiveness (PEM+ min-max and mean percent completion rate, mean completion time, and mean task difficulty rating), and USE summary scores (mean and range) for ease of use, ease of learning, and user satisfaction.

Aim 2 Statistical Plan:

All analyses were completed on the total sample and age subgroups (0-3 years, 4-5 years) using SPSS 24.0. The primary study aim was to assess for PEM+ feasibility and acceptability. To assess for PEM+ feasibility, retention rate, median completion time of first iteration, median completion time of subsequent interactions, and use of tiered support were reported. To assess for PEM+ acceptability, total scores were reported as means with standard deviations. Additionally, open-ended responses were independently coded by four research team members to sort caregiver feedback regarding the acceptability of PEM+ into categories.

As a secondary aim, preliminary effects mean self-efficacy item scores were calculated and Pearson correlations were used to ascertain associations between proportion of care plans created, relative to areas of desired change, with caregiver self-efficacy scores.

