2.0 Background/Scientific Rationale

- *Describe the research problem and provide rationale for the research.*

The goal of the proposed research is to achieve a major advance in promoting effective and efficient delivery of pediatric occupational therapy services for young children with developmental disabilities. To evaluate PEM-Plus usability (Aim 1), ten parents will be recruited to perform tasks related to navigating the PEM-Plus interface. Data on completion rate and time, and user satisfaction, will be analyzed to guide PEM-Plus improvements. Then, in Aim 2, we will examine the feasibility and scientific basis for using the revised PEM-Plus to improve goal setting, care plan development, and parental self-efficacy. Study results will yield a final version of PEM-Plus that is ready for larger-scale testing in a pediatric efficacy trial. This project is aligned with the newly released AOTF research priority of improving care coordination towards improved participation in meaningful activities.

- *Briefly summarize prior experience and/or history relevant to the research.*

Members of our research team pioneered some of the first participation and environment measures that are commonly used in pediatric research and practice (Sections 1.3 and 1.4). The PEM approach represents a significant departure from prior efforts to measure children's participation because we explicitly combined the assessment of children's participation and environment within the same instrument. Development of a web-based application to help parents participate in planning their child's care is a highly innovative and logical next step for our research team. To our knowledge, no other group has developed a web-based application to empower and assist parents in developing their own solutions to promote their child's participation. We expect that PEM+ can advance the quality and efficiency of care planning in pediatric occupational therapy to achieve participation-level outcomes. Our multi-site, transnational research team has established an 8-year track record of continuous extramural funding. We developed and tested the PEM-CY and YC-PEM for research purposes and built a Knowledge Hub to facilitate knowledge uptake and resource exchange about children's participation and environment among key stakeholders (researchers, parents, and providers). We believe that PEM+ will significantly improve the uptake of the PEM approach in practice.

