6.0 Study Design and Procedures

- *List any collaborating sites where human subjects research will be performed, and describe the role of those sites and collaborating investigators in performing the proposed research (if applicable).*
- *Describe the study design. The description should be capable of meeting the study objectives.*
- *Provide a thorough description of all study procedures, assessments and subject activities in a logical and sequential format.*
- *Indicate what study activities happen when and where, including, when applicable, a study schedule that notes number and length of study visits for subjects, such as any of the following:*
 - *Screening for eligibility*
 - *Enrollment/baseline*
 - *Treatment/Intervention period*
 - *Follow-up*
 - *Final study visit*
 - *Early termination visit*
 - *Unscheduled visits*
- *Indicate which procedures are standard of care and which procedures are being done for research purposes.*

There are 2 aims to this year long project. All tasks are being performed for research, not service provision.

Aim 1 data source: In addition to demographic data, numerical and narrative data will be stored with unique ID number on the backend of the PEM+ platform (secure, password-protected and backed up to central server daily) during data collection and then exported and stored as an SPSS file for access by the UIC team.

We will opt to administer SEQ after every individual task. We will assess for Ease of Use, Ease of Learning, and Satisfaction at the end of PEM+, using the USE that estimates user satisfaction based on response to items on ease of use, ease of learning, and satisfaction (22 questions, each using a 7 point scale from [1] strongly disagree to [7] strongly agree). We will assess for overall ease using the SEQ after every individual task (1 question, using a 7 point scale from [1] very difficult to [7] very easy.

Mean percent completion and task completion time will be computed for each task. Narrative data will be exported and stored as an MS Word file and content analyzed using NVivo 11.0 in order to identify recurrent points of user feedback to guide PEM+ revisions.

Aim 1 Sampling and Data Collection:

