For participants coming from Blue Bird Day School, those who sign a consent will fill out electronic forms for the YC-PEM and demographic information. Upon receipt, research staff will create a user account and manually enter consent, demographic, and YC-PEM data for the participant into the REDCap platform. Participants will be emailed a weblink to access their YC-PEM summary report when ready along with a link to begin the PEM+ usability test.

The PEM+ usability test will take 60 minutes and involve having participants complete a series of 8 tasks that correspond to key functions of PEM+ (e.g., you decide to go to sleep and wish to exit the platform after completing Step 1. Save your progress and log off). Following task completion, participants will complete the Single Ease Question (SEQ) after every individual task, while Usefulness, Satisfaction, and Ease of Use (USE) will be administered at the end of PEM+ to all participants. Each participant will receive a \$20.00 mailed payment.

For each of the 8 tasks, we will assess for Ease of Use, Ease of Learning, and Satisfaction at the end of PEM+, using the USE that estimates user satisfaction based on response to items on ease of use, ease of learning, and satisfaction (22 questions, each using a 7 point scale from [1] strongly disagree to [7] strongly agree). We will assess for overall ease using the SEQ after every individual task (1 question, using a 7 point scale from [1] very difficult to [7] very easy).

Aim 2 data source: There are 4 elements being assessed in this aim. For Process, data are derived via web analytics to ascertain recruitment and retention rates according to child's age. For Resources, data are also derived via web analytics for information about PEM-Plus completion time per iteration. For Management, web analytics are used to examine frequency and duration of tiered coaching (tier 1: videos, tier 2: email/text, tier 3: phone /Skype chat) and online progress notes entered into the platform by coaches are obtained to estimate type of support. For Scientific basis (preliminary effects), data sources are as follows: 1) web analytic data are used to estimate number of goals set and strategies developed in 4 weeks, and 2) modified CanChild Survey completion at 4 weeks is used to estimate perceived effectiveness of PEM-Plus for goal setting and strategy development

Aim 2 Sampling and Data Collection:

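### Does the Aim 1 SAP lose the protocol's task-by-task usability results, so that the analysis cannot show which PEM+ function to revise?

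*SAP*

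**What the plan says.** Protocol section 2.0 gives the purpose of the Aim 1 data: "Data on completion rate and time, and user satisfaction, will be analyzed to guide PEM-Plus improvements". Aim 2 then uses the revised PEM-Plus.

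Protocol section 6.0 sets the design and the level of analysis. Participants "complete a series of 8 tasks that correspond to key functions of PEM"+, and the target sample is 10. On the computation it says "Mean percent completion and task completion time will be computed for each task". On the ease rating it says "We will opt to administer SEQ after every individual task". Narrative data are to be content-analysed "in order to identify recurrent points of user feedback to guide PEM+ revisions".

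The SAP (Aim 1 Statistical Plan) reports demographics and YC-PEM scores user by user. It then derives usability estimates "for the total study sample, according to technical effectiveness (PEM+ min-max and mean percent completion rate, mean completion time, and mean task difficulty rating", followed by mean and range for the USE scores. It does not repeat the per-task wording, does not give the unit of the min-max, and does not mention the narrative analysis under Aim 1.

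**The concern.** Aim 1 exists to decide what to revise before the feasibility test. A reader who has only the SAP could take the completion rate, completion time and difficulty rating as single figures for PEM+ as a whole. Such figures can look the same when one function is broken and when a few errors are scattered over all functions, although the two situations call for different revisions. An undefined min-max adds to the doubt, since two analysts could produce different ranges from the same data. The Aim 1 paragraph also leaves out the narrative analysis, so the SAP alone offers no other route to the weak function.

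**Working it through.** Neither document gives an Aim 1 sample-size, power or precision figure, so there is nothing to reproduce. The check has two parts: whether pooled figures would hide the problem, and whether the plan really calls for pooled figures only.

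**Part 1: would pooled figures hide a weak task?**

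Inputs: 10 users (target) and 8 tasks, both from protocol section 6.0, so 10 × 8 = 80 attempts. Completion is assumed to be yes/no for the illustration. The documents speak of percent completion and do not define it that way.

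- Pattern A: one task completed by 2 of 10 users, the other seven by all 10. Overall = (7 × 10 + 2)/80 = 72/80 = 90%.
- Pattern B: eight users each fail a different task. Overall = (8 × 9)/80 = 72/80 = 90%.

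| | Overall | Per-user min-max | Per-task min-max |
|---|---|---|---|
| A | 90% | 7/8 to 8/8 = 87.5% to 100% | 20% to 100% |
| B | 90% | 7/8 to 8/8 = 87.5% to 100% | 90% to 90% |

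The overall mean and the per-user range cannot tell A from B. A range over tasks can, but it does not name the task. With five failures by five different users, the overall mean is 75/80 = 93.75% and the per-user range is 87.5% to 100%, whether all five fall on one task or on five tasks.

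The ease rating behaves in the same way if pooled. Seven task means of 6.5 and one of 2.0 (illustrative values) average (7 × 6.5 + 2.0)/8 = 47.5/8 = 5.9 on the 7-point scale.

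So the arithmetic of the concern is right, on the condition that only pooled figures are produced.

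**Part 2: does the plan call for pooled figures only?**

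- *Completion and time.* Protocol section 6.0 commits to per-task computation without qualification. The SAP is silent on tasks. Silence in a one-paragraph summary does not cancel an explicit commitment in the protocol, and the two statements can both be carried out.
- *Total study sample.* In the SAP this phrase follows a sentence about reporting for each user. The contrast is between individual and grouped participants. A mean for one task over all users is still an estimate for the total sample.
- *Difficulty rating.* The SAP calls it a task rating and the SEQ is asked after each task, so a mean per task is a natural reading.
- *Min-max.* If it runs over tasks, the eight task rates have to be computed first. If it runs over users, the protocol's task rates are still due. Either way the per-task figures exist, and the table label settles the unit.
- *Narrative feedback.* The content analysis is planned in the protocol for the express purpose of guiding revisions. A statistical paragraph that omits a qualitative analysis does not remove it.

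**Timing.** The SAP is dated June 17, 2017 and is written in the past tense. The protocol places Aim 1 in Months 1-5 of a project that starts on 7/1/2016, that is, July to November 2016. On that schedule the revisions came before the SAP, so its wording could not have steered them.

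**The case for a change.** The strongest reply is that the SAP is where the reported estimates are specified, and that it attaches a PEM+ label to completion with an undefined range. Two analysts working from it alone could present different tables, and the remedy would be one table and one sentence from data already collected. It is true that the SAP is looser than the protocol and that the unit of the min-max is not stated. But that is missing detail which the protocol supplies for completion and time, and no analyst holding both documents is led to a wrong result.

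The further suggestions add little. Counting completions out of 10 assumes a yes/no measure and a fixed denominator, whereas the protocol has percent completion and a target of 10; such a table could replace the planned measure with another one.

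Adding the median and range to mean time is a preference. The SAP does use medians for Aim 2 ("median completion time of first iteration, median completion time of subsequent interactions"), but the protocol's own Aim 1 wording suggests a mean, so the mean is no departure. The argument for the median rests on idle time that the documents do not describe. If one user of ten paused for 15 minutes, the mean of a 60-minute session ("The PEM+ usability test will take 60 minutes") would become (9 × 60 + 75)/10 = 61.5 minutes. The mean of a 7.5-minute task (60/8, assuming equal tasks) would become (9 × 7.5 + 22.5)/10 = 9.0 minutes.

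Per-task rates from ten users are also coarse. The exact 95% interval is 19% to 81% for 5/10 and 55% to 99.7% for 9/10. They can point to a function worth a closer look, alongside the comments, but they cannot rank the functions.

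**Conclusion.** The concern does not hold as a fault in the analysis. Pooled figures alone could hide a weak function, with the same 90% and 87.5% to 100% in two opposite situations, but the plan does not restrict itself to pooled figures. The protocol requires completion and time for each task, the SEQ is collected for each task, and narrative feedback is analysed to guide revisions. The SAP's shorter wording is a gap that analysts fill sensibly from the protocol. Repeating the per-task phrase and naming the unit of the min-max would be harmless, but it would not change what is computed or any conclusion.

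This rests on reading the protocol and the SAP together, and on the protocol's per-task statement still being in force; nothing in either document withdraws it. The stakes are limited to the presentation of a descriptive usability test in a target sample of 10.

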3.0 Objectives/Aims

- *This section helps to clarify the questions the researcher expects to answer*
 - *Identify hypotheses being tested/primary endpoints/primary purpose of the protocol*

Aim 1 Objective: Examine the usability (technical effectiveness, efficiency, and user satisfaction) of the PEM+ interface by parents of young children with developmental disabilities and delays (Months 1-5).

Aim 2 Objective: Examine PEM+ feasibility and preliminary effects for goal setting and care planning (Months 6-12).

Hypothesis: Based on our prior intervention research to promote participation among children with physical disabilities, we expect that PEM+ will initially take up to 4 weeks with more intensive coaching support needed to generate viable activity-specific goals and action plans, and less time in subsequent iterations. There will be no significant age group differences in PEM+ feasibility.

- *Describe secondary endpoints (if applicable)*
- *Substudy endpoints (if applicable)*
- *Study duration*
- **Per funder guidelines, this project will be completed between 7/1/2016-6/30/2017.**

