We will build on Aim 1 recruitment strategies to recruit 24 parents of children with developmental disabilities ages 0-3 years for PEM+ feasibility testing. The sample size estimate is similar to prior studies on participation outcomes (Verhoef, Miedema, Van Meeteren, Stam, and Roebroeck, 2013) and feasibility considerations. We will target recruitment of children in 1 age group (infants and toddlers between 0-3 years) to examine the feasibility of PEM+. Inclusion criteria: Same as Aim 1.

Automated email with study flyer will be sent to families on listserves. Parents who meet eligibility criteria will be directed via web link to create a user account to enter the YC-PEM study platform that is being hosted on REDCap at UIC. Participants will provide online consent and then proceed in completing a demographic questionnaire and YC-PEM online to receive a summary report, followed by phone consultation to interpret their report. Participants will then click a web link on the YC-PEM report to be directed to a revised PEM+ platform hosted via combination of Amazon cloud and REDCap at UIC. Participants will proceed through PEM+ to apply information from the report to generate participation goals for their child and potential intervention strategies. Parents will be given 4 weeks to develop as many goals and intervention strategies as possible, and they may opt for help using one or more of the following options for support: 1) text-based examples of priorities, goals, and strategies that are accessed by the parent in the PEM+ platform, 2) email coaching support (parent clicks on a link in the platform to email trained UIC staff with questions), and/or 3) phone or video conferencing (Skype) consult that participant can request in the platform, to be provided by master coach ([name]). No more than 6 participants will begin PEM+ each week to ensure feasibility, resulting in a total of 8 weeks for data collection (6 participants/week x 4 weeks/participant). Weekly text-message and email reminders will be issued to all participants to promote retention and completion rates. Final phone consultation and CanChild survey completion will take place at 4 weeks. Each participant will be paid \$80.00 at 4 weeks (\$40.00 prorated payment for completion of no more than 2 weeks).

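### Aim 2 completion time: two unlinked medians inside one 4-week window can look like faster later use when only the contributing parents differ; a finisher count and a within-parent ratio would answer the question better (minor)

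*SAP*

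**What the plan says.** Protocol section 3.0 sets the expectation in two parts: "we expect that PEM+ will initially take up to 4 weeks with more intensive coaching support needed", "and less time in subsequent iterations". Section 6.0 gives each of the 24 Aim 2 parents a single window, "Parents will be given 4 weeks to develop as many goals and intervention strategies as possible", and closes it: "Final phone consultation and CanChild survey completion will take place at 4 weeks". On the source of the times it says "data are also derived via web analytics for information about PEM-Plus completion time per iteration".

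The SAP's Aim 2 plan puts completion time under its primary aim, next to retention and use of tiered support, and reports it as "median completion time of first iteration, median completion time of subsequent interactions". On who is analysed it says only "All analyses were completed on the total sample and age subgroups".

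Neither document gives the unit of time (elapsed days or active time on the platform), the start and stop of an iteration, who enters each median, or how an iteration unfinished at 4 weeks counts. The SAP writes *interactions* where the protocol writes *iterations*; I read them as the same thing. Protocol sections 9.0 and 12.0 contain only template prompts.

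**The concern.** The two medians need not describe the same parents. Only a parent who finishes a first iteration with time left can contribute a later one, and a fast parent may contribute several. The later median is therefore drawn from a faster group. Set beside the first, it can suggest that parents speed up when nothing has changed within any parent.

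The window adds a ceiling. If time is elapsed days and only finished iterations count, the first median cannot exceed 28 days whatever the truth, so it cannot contradict an expectation of up to 4 weeks.

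Completion time supplies two of the four feasibility items under the SAP's primary aim, and protocol section 2.0 says the results should make PEM+ ready for a larger efficacy trial. A comfortable-looking first median, or an apparent learning effect, could carry over into the planning of that trial.

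**Working it through.** **Inputs from the documents.** 24 parents; at most 6 starts per week; one 4-week (28-day) window per parent. The plan gives no completion-time figure to reproduce. Its calendar does reproduce: 24/6 = 4 start weeks, plus a 4-week window, is the 8 weeks stated in section 6.0.

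**Assumptions, not in the documents.** Elapsed days; finished iterations only; iterations back to back; log-normal times; between-parent/within-parent log-SDs of 0.4/0.2, 0.6/0.3 and 0.3/0.5. The total log-SD is s = √(between² + within²) = 0.447, 0.671 and 0.583.

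**Step 1: the ceiling on the first median.** With true median m, the proportion finishing by day 28 is p = Φ(ln(28/m)/s), and the median among finishers is m·exp(s·z(p/2)). For m = 28, p = 0.50 and z(0.25) = −0.674, so the finishers' median is 28·exp(−0.674·0.447) = 20.7 days for the first SD pair, and 17.8 and 18.9 days for the others.

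| True first median | Finish by day 28 | Median among finishers |
|---|---|---|
| 21 days | 67-74% | 15.7-18.1 days |
| 28 days | 50% | 17.8-20.7 days |
| 35 days | 31-37% | 19.2-22.2 days |

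In the last row about two thirds of parents fail to finish in 4 weeks, and the reported figure is still about 3 weeks.

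**Step 2: apparent shortening with no true change.** Simulated trials of 24 parents, with later iterations as long as the first on average:

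| True length per iteration | Second median below first | Mean parents with both finished |
|---|---|---|
| 1-3 days | about 50% (no lean) | 23.8-24 |
| 7 days | 61-72% | about 21-22* |
| 14 days | 89-100% (14-21 days together) | 10.8-11.8 |
| 21 days | as above | 3.8-6.1 |

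*From the second set of assumptions below.

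The median within-parent second-to-first ratio falls below 1 in about half of these trials, as it should when nothing changes.

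A second set of assumptions (log-SD 0.6, within-parent correlation 0 to 0.5) gives the same picture: 57-66% at 7 days, 85-93% at 14 and 89-97% at 21. At 14 days the second and first medians are 10.0 and 12.7 days (ratio 0.79) to 9.4 and 12.7 (0.74). At 21 days they are 11.2 and 16.4 (0.68) to 10.5 and 16.4 (0.64).

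**Step 3: pooling.** If every later iteration enters one pooled median with no limit on their number, the lean appears even at 1-3 days: 79-100% of trials, against 48-58% with one value per parent. At short lengths the cause is fast parents counting many times, not the 28-day limit.

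**Step 4: does the remedy work?**
- Ranking unfinished *first* iterations above 28 days recovers true medians of 7, 14 and 21 days.
- Doing the same for *second* iterations overcorrects. With a true 14 days and no change, the median among those who started a second one becomes 16.1 days or exceeds 28, depending on the correlation. The second clock starts only after the first iteration time T1, so an unfinished second iteration is known only to exceed 28 − T1 days.
- The paired ratio is 1.00-1.02 with no change, but it is pulled towards 1 otherwise: a true 2.0 reads 1.65-1.93 at 14 days and 1.60-1.91 at 21 days, and a true 0.6 reads 0.60-0.74.

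**The case against.** The strongest reply is that the SAP only describes. It reports the medians to assess feasibility and names no hypothesis, test or contrast. A reader might infer that Aim 2 tests the expectation of shorter later iterations by comparing the two medians; the SAP does not say so. What stands is narrower: no other planned completion-time figure bears on that expectation, so a reader who wants an answer will compare them.

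Second, the ceiling needs both elapsed days and finished-only counting. Neither is stated, and web analytics listed under resources could equally mean active time. An expectation in weeks favours elapsed days for the hypothesis, but does not fix what the platform records. With active minutes the ceiling largely disappears, and the 4-week expectation then has no figure addressing it.

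Third, the large effects need iterations of 14-21 days. A design that asks for as many goals as possible in 4 weeks may well have short ones, and an upper limit of 4 weeks does not show that 2-3 weeks is typical. A reader might infer from the pooled result that the lean exists at every length. That depends on pooling unlimited iterations, which the SAP does not specify.

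Fourth, non-completion would not be wholly hidden. Retention, the counts of goals and strategies, and the proportion of care plans relative to areas of desired change all show part of it. None says how an unfinished iteration enters a median.

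**Conclusion.** The point stands as a cheap improvement of minor severity. The plan's two medians can rest on different parents, share one 28-day window, and carry no rule for unfinished iterations. On elapsed days in finished iterations, the first median is capped at 28 days. On that reading, with the assumed log-normal times, apparent shortening without real change is strong at 14-21 days per iteration, modest at 7 days and absent at 1-3 days unless all later iterations are pooled. The iteration lengths and spreads are assumptions, and the documents do not show which range applies. They therefore do not support saying that the reported medians are biased, only that they could be and that a reader could not tell.

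**What to change.** Four additions, all from per-iteration web analytics that the protocol already collects:

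1. **First iteration.** Report the number finishing by day 28 out of all who started, with an exact 95% CI (for illustration, 9/24 = 38%, CI 19-59%). Show drop-outs separately from retained parents who did not finish; the protocol's prorated payment foresees early leavers. Give the elapsed-day median over all starters with unfinished first iterations ranked above 28 days, or *not reached* if under half finish (a plain number needs 13 of 24). Report active time separately if it is recorded.
2. **Later iterations.** Beside the planned medians, report the median within-parent second-to-first ratio with the number of pairs. Use one value per parent for later iterations. Give a CI for the ratio only with at least 6 pairs: the widest sign-based interval covers 1 − 2·0.5⁵ = 93.8% with 5 pairs and 96.9% with 6.
3. **Unfinished second iterations.** Do not rank these above 28 days. List each as exceeding 28 days minus the first-iteration time, and keep parents who never started a second one separate, since they may have had no further goal.
4. **Definitions.** State the time unit and the start and stop of an iteration, and reconcile *interactions* with *iterations*.

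The cost is a few sentences. Because the SAP is in the past tense, they may belong in the report rather than in an amended plan. There are real downsides. The first-iteration figure becomes less favourable. The ratio rests on about 4-6 of 24 parents at 21 days with no change, and on 0.7-2.4 with a twofold slowdown, where 8-52% of trials have no pair at all. It also understates a true slowdown, so it is weakest where the lean is largest and should be read with its number of pairs.

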4.0 Eligibility

- *Identify the subject population being evaluated by the protocol.*
- *Indicate the source of subjects.*
- *Identify who will assess and determine subject eligibility.*

Participants will be issued automated emails with study flyers to self-enroll in both aims of the project. Hence, all recruitment comes from UIC ([name]). Participants will self-enroll in the study and complete screening questions online to confirm eligibility. This confirmation of study eligibility will take place prior to online informed consent. We have successfully piloted this process in an NIH-funded pilot proposal, resulting in

enrollment of 39 study subjects in a 2-month period (IRB approval obtained in Colorado, at PI's prior institution, and is active from 2015-2016).

- *Indicate how and where eligibility will be documented.*

Participant confirms his/her eligibility based on a set of screening questions (e.g., what is your primary language, What is your child's date of birth, for how long has your child been receiving services). The portal and platform will no longer be hosted by Northwestern University. All data collected, including documenting participants who confirm their eligibility to enroll, via the web-based application that is being hosted via an Amazon cloud account will be pushed and stored in REDCap at UIC via API.

- *Attach an eligibility checklist to the protocol.*

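### The SAP for Aim 2 leaves out the goal and strategy counts and the recruitment rate that the protocol names, and attaches the preliminary-effects label to self-efficacy scores whose items and time point are not stated

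*SAP*

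**What the plan says.** **Protocol.** The Aim 2 objective in Section 3.0 is "Examine PEM+ feasibility and preliminary effects for goal setting and care planning". Section 6.0 (Aim 2 data source) sets out what is measured under four elements:

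- Process: "data are derived via web analytics to ascertain recruitment and retention rates according to" the child's age.
- Resources: PEM+ completion time for each iteration.
- Management: how often, for how long and in what form tiered coaching is used.
- Scientific basis, which the protocol equates with preliminary effects, has two numbered sources. The first is that "web analytic data are used to estimate number of goals set and strategies developed in 4 weeks". The second is that "modified CanChild Survey completion at 4 weeks is used to estimate perceived effectiveness of PEM-Plus for goal setting and strategy development".

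The Aim 2 procedures in the same section give the instruction behind the counts: "Parents will be given 4 weeks to develop as many goals and intervention strategies as possible". Self-efficacy appears once in the protocol, in Section 2.0, as one of three things the revised PEM+ is meant to improve. No measure is attached to it there.

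**SAP, Aim 2 Statistical Plan.** For feasibility, "retention rate, median completion time of first iteration, median completion time of subsequent interactions, and use of tiered support were reported". For acceptability, total scores from an unnamed instrument are given as means and standard deviations, and open-ended comments are coded. For the secondary aim: "As a secondary aim, preliminary effects mean self-efficacy item scores were calculated". A Pearson correlation then relates those scores to care plans as a share of the areas where the caregiver wanted change.

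**The concern.** The two documents use the same label for different quantities. In the protocol, preliminary effects means what parents produced with the tool and how effective they found it for that purpose. In the SAP, it means average self-efficacy item scores. The production counts do not appear in the SAP, and neither does recruitment rate.

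Two things are at stake. First, goals and strategies are the direct output of what parents were asked to do, so they bear most closely on the stated objective. Recruitment rate matters for planning the larger efficacy trial that Section 2.0 says should follow. A report written from the SAP alone could omit all of these.

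Second, a mean score from one group, labelled as an effect and with no stated time point or baseline, invites a reading it cannot support. A reader planning the next trial could take it as evidence that PEM+ raised self-efficacy.

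**Working it through.** The plan gives no figure to reproduce on this point. The check is a comparison of the two texts.

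**Step 1. Outcomes side by side.**

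| Protocol Section 6.0, Aim 2 | SAP, Aim 2 |
|---|---|
| Recruitment rate | Not mentioned |
| Retention rate | Listed |
| Completion time per iteration | Listed (first and later iterations) |
| Tiered coaching: frequency, duration, type | Listed only as use of support |
| Goals and strategies in four weeks | Not mentioned |
| CanChild perceived effectiveness at four weeks | Not named; may be the acceptability total scores |
| No self-efficacy measure described | Mean item scores, labelled preliminary effects |

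**Step 2. Does the care-plan proportion stand in for the counts?** The SAP uses the proportion only as one side of a correlation and lists no summary of it. Even if it were summarised, proportion = plans created / areas of desired change, and the count cannot be recovered from that ratio: 2/4 = 0.50 and 10/20 = 0.50. Two parents with a fivefold difference in output get the same value.

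**Step 3. When and how could self-efficacy have been measured?** At Aim 2 entry, Section 6.0 describes a demographic questionnaire and the YC-PEM. At four weeks it describes a final phone consultation and the CanChild survey. The appendix line names demographic, YC-PEM and CanChild questionnaires, whose items are not in the text. The self-efficacy items could belong to one of these, but neither document says so. No baseline self-efficacy measure is described. On its plain wording, the SAP's mean item score is a level, not a change.

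**Step 4. What denominator is available for recruitment?** Section 6.0 gives 832 families with children aged 0-3 years on one listserve, under Aim 1, and says that Aim 2 builds on the Aim 1 strategy. It adds a Chicago day school without a count. Section 5.0 speaks of two listserves and Section 13.2 of one. So 832 is relevant but is not a complete Aim 2 denominator. The target of 24 parents over 832 (24/832 = 2.9%) is a planned number over one source and should not be read as a recruitment rate. Section 4.0 says the stored data include "documenting participants who confirm their eligibility to enroll", so enrolled / confirmed eligible may be computable. That ratio is a consent rate among people who had already chosen to visit the site, and it would overstate recruitment.

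**Step 5. Timing.** The SAP is dated 17 June 2017 and is written in the past tense. Section 3.0 gives the project end as 30 June 2017, which is 30 - 17 = 13 days later. Any summary added now may be chosen with data in view, so its source should be shown.

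**The case against.** The strongest reply is that nothing is lost. The protocol still specifies the counts and their data source, nothing says the SAP replaces it, preliminary effects are only a secondary aim in the SAP, and the care-plan proportion is a care-planning output. This partly stands: the data were planned for collection, and the objective is touched. But the SAP is the document that says what will be summarised, and Step 2 shows the proportion is not a substitute.

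A second reply is that Aim 2 has one group by design, and the protocol itself uses preliminary effects for single-group quantities without a baseline. That is right. The lack of a comparator is not a SAP error, and the goal and strategy counts are no better placed than self-efficacy to isolate an effect. Any caveat must cover all of them.

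Three stronger readings are tempting, and the documents do not support them:

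- That self-efficacy was swapped in for the planned outcomes. Section 2.0 already names it as a target of Aim 2; what is missing is how and when it was measured.
- That the CanChild outcome was dropped. The unnamed acceptability total scores may be that survey.
- That no self-efficacy instrument exists. The questionnaires attached to the protocol are not shown, so the text can establish only that the SAP does not name one.

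**Conclusion.** The concern holds in a limited form. The SAP does not report the goal and strategy counts or the recruitment rate that the protocol names for Aim 2. It applies the preliminary-effects label to self-efficacy scores without stating their items or time point, and the available text describes no baseline.

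The size is best stated in words. A fraction of outcomes omitted would depend on whether goals and strategies count as one item, as the protocol numbers them, or two. Under the SAP as written, the first of the two numbered preliminary-effects sources is absent and the second cannot be identified by name.

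The conclusion assumes that no further analysis document exists and that the attached questionnaires do not themselves settle the self-efficacy time point. In a feasibility study of 24 parents, with the data source already specified, this should be corrected, but it does not undermine the study.

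**What to change.** Add the following to the SAP as descriptive summaries, citing the Aim 2 data-source text in Protocol Section 6.0 as the source of items 1 and 3:

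1. Goals and strategies per parent over four weeks, as median and IQR, for all parents who started PEM+.
2. The care-plan proportion itself, not only its correlation with self-efficacy.
3. Recruitment rate with its denominator stated: families sent the flyer, if that count was kept. Report enrolled / confirmed eligible separately and call it a consent rate.
4. The name of the instrument behind the acceptability total scores, and whether it is the CanChild survey.
5. The self-efficacy items and time point, reported as a score at that time and not as an effect, unless a baseline on the same items exists.
6. A sentence stating that no single-group Aim 2 summary, including the counts, isolates an effect of PEM+.

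Mark any summary form that was chosen after data were seen.

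The cost is a few lines of text and simple summaries of data already planned for collection, with no new participants or procedures. The count of families contacted is not documented as kept and may be unavailable; if so, the SAP should say so. The downside is slightly more reporting and a less favourable label for the self-efficacy result.
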